3.2 Primary Study Endpoints

- Efficacy of quinine and saline irrigations compared to saline irrigations alone.
- Changes in quality of life (SNOT-22 questionnaire) (both composite and subscale scores)
- Nasal endoscopy (Lund-Kennedy Score)
- Alterations in microbiology recovered (as determined by sinus microbiology culture)
- Whether or not conventional antibiotics were needed to treat the infection during or following the irrigation trial (as prescribed as part of routine care)

CONFIDENTIAL

3.3 Secondary Study Endpoints

- Changes in olfaction as quantified with the Sniffin' Stick-12 score [administered as part of research]
- Pre and post treatment CT scan as scored by the Lund-MacKay CT scoring system¹⁹. These scores will only be available if CT scans are clinically indicated at the time of baseline and/or 12-week post clinical visits.
- Alterations in the Sinonasal microbiome (conducted as part of an ongoing research project)

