2.2. Secondary Outcome Variable(s)

The secondary outcomes variables are:

- Pre- and post-treatment Sniffin' Stick-12 (Burghart Instruments, Wedel, Germany) score.
- Pre- and post-treatment CT scan scored with the Lund-MacKay CT scoring system¹⁹ by a blinded investigator. The CT scans at pre and post will only be done if clinically indicated by the physician.
- Pre- and post-treatment microbiome analysis
- Pre-treatment taste test to determine bitter taste sensitivity

3 Study Design

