4.4.2 Data Collection and Follow-up for Withdrawn Subjects

Even though subjects may be prematurely withdrawn from the study, it is imperative to collect infection data (microbiology swabs) or symptomatic data. Such data is important to the integrity of the final study analysis since early withdrawal could be related to the tolerability profile or the ineffectiveness of the therapy. If a subject withdraws consent to participate in the study, attempts should be made to obtain permission to follow up with the subject's CRS for the duration of the 12-week follow-up period. Subjects with incomplete/missing data will not be included in the analysis.

5 Study Drug

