6.2 Visit 2 (week 4, +/- 7 days)

Subject is asked to return to the clinic where they will be subjected to the same procedures at Visit 1. The clinical research nurse will measure and record the volume of nasal spray remaining in the stock bottle to determine compliance. No CT scan will be performed at the 2nd visit.

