6.3 Visit 3 (week 12, +/- 14 days)

Subject is asked to return to the clinic where they will be subjected to the same procedures at Visit 1. A CT scan will only be performed if clinically indicated by the physician.

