6.5 Statistical Methods

Data will be analyzed after 100 subjects have completed the study. Descriptive demographic data will be compiled including mean and median age, adjuvant therapy use, use of oral antibiotics, and microbiome profile. Longitudinal linear mixed effects modeling will be used to examine the relationship between all outcome measures and treatment assignment, assuming that the distribution of the outcome measures follow a unimodal symmetric distribution and satisfies the assumptions for mixed effects modeling. Mixed effects modeling takes advantage of all available data (up to the point of loss to follow-up or withdrawal) and also can address missing data. As long as the level of missingness is not excessive and patterns of missingness are not detected, mixed effects modeling can use all available data.²¹⁻²⁴ For all analyses, alpha will be set to 0.05 (two-sided).

The Epidemiology Department may be consulted at the completion of the study to assist with data analysis. Only de-identified data will be provided. No PHI will be shared.

CONFIDENTIAL

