6.6 Subject Population(s) for Analysis

All-randomized population: Any subject randomized into the study, regardless of whether they received study drug, will be analyzed.

7 Safety and Adverse Events

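### The Lund-Mackay CT endpoint is observed only when a scan is clinically indicated, yet Section 6.5 compares it between arms like any other outcome and gives no fallback when missingness is patterned

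*Combined protocol and SAP*

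**What the plan says.** Section 2.2 lists the pre- and post-treatment Lund-Mackay CT score, read by a blinded investigator, as a secondary outcome, and adds: "The CT scans at pre and post will only be done if clinically indicated by the physician". Section 3.3 repeats the limit for the endpoint: "These scores will only be available if CT scans are clinically indicated at the time of baseline and/or 12-week post clinical visits". Sections 3.1 and 6 (visit table) carry the same condition. At week 4, "No CT scan will be performed at the 2nd visit" (Section 6.2). At week 12, "A CT scan will only be performed if clinically indicated by the physician" (Section 6.3). So the only possible post-treatment score comes from week 12, at the physician's discretion.

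On analysis, Section 6.5 says: "Longitudinal linear mixed effects modeling will be used to examine the relationship between all outcome measures and treatment assignment". Alpha is two-sided 0.05 for all analyses. CT has no separate method, descriptive status or sensitivity analysis. Section 6.5 allows the use of all available data on a condition: "As long as the level of missingness is not excessive and patterns of missingness are not detected". It does not say what is done if the condition fails.

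Two further rules bear on missing data. Section 4.4.2, on withdrawn subjects, says: "Subjects with incomplete/missing data will not be included in the analysis". Section 6.6 says: "Any subject randomized into the study, regardless of whether they received study drug, will be analyzed".

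**The concern.** Randomization makes the arms comparable as randomized. It does not make the subsets with a week-12 CT comparable, because membership is decided after treatment by a physician who sees how the patient is doing. If quinine relieves the symptoms that lead to a scan, fewer quinine patients are scanned, and those who are will be the ones who responded least. Comparing scanned with scanned then mixes the treatment effect with selection.

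Blinding and blinded scoring do not remove this, since the selection runs through the patient's condition and not through knowledge of the arm. A mixed model would remove it only if the data in the model fully explained why a scan was ordered, and Section 6.5 does not arrange for that. Selection at the baseline scan is a lesser matter: it precedes treatment, so it costs precision and generalizability but does not itself bias the arm comparison.

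At stake is the reading of one secondary endpoint in a trial that Section 6.4 describes as a guide for future studies.

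**Working it through.** **The plan's own figure.** There is none for CT. The one sample-size calculation (Section 6.4) concerns SNOT-22 and reproduces: with SD 20 and half-width 10, n per group = 2 × (1.96 × 20 / 10)² = 30.7, and with the t quantile the smallest n is 32 (half-width 9.995). It is unaffected by this point.

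**Inputs, all assumed because the documents give none.** True CT effect Δ = -0.5 SD; correlation r = 0.3 or 0.6 between CT severity and the symptoms that prompt a scan; a week-12 scan when symptoms exceed a threshold t; 20%, 30% or 50% of placebo patients scanned.

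**Formula.** With CT and symptoms bivariate normal, and symptoms lowered by δ SD on quinine, the expected difference among scanned patients at week 12 is

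D = Δ + r × [λ(t + δ) - λ(t)], where λ(x) = φ(x) / (1 - Φ(x)) and 1 - Φ(t) is the placebo scan rate.

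Two cases: (a) symptoms move only through CT, so δ = 0.5r; (b) symptoms shift by a full δ = 0.5.

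Worked example, 20% scanned and r = 0.6: t = 0.842 and λ(t) = 1.400.
- Case (a), δ = 0.30: λ(1.142) = 1.640, so D = -0.5 + 0.6 × 0.240 = -0.356, a loss of 0.144 / 0.5 = 29%.
- Case (b), δ = 0.50: λ(1.342) = 1.805, so D = -0.5 + 0.6 × 0.405 = -0.257, a loss of 0.243 / 0.5 = 49%.

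| r | Placebo scanned | (a) quinine scanned | (a) D | (a) loss | (b) quinine scanned | (b) D | (b) loss |
|---|---|---|---|---|---|---|---|
| 0.3 | 20% | 16% | -0.464 | 7% | 9% | -0.378 | 24% |
| 0.3 | 30% | 25% | -0.466 | 7% | 15% | -0.384 | 23% |
| 0.3 | 50% | 44% | -0.471 | 6% | 31% | -0.397 | 21% |
| 0.6 | 20% | 13% | -0.356 | 29% | 9% | -0.257 | 49% |
| 0.6 | 30% | 20% | -0.364 | 27% | 15% | -0.269 | 46% |
| 0.6 | 50% | 38% | -0.380 | 24% | 31% | -0.294 | 41% |

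**Limits of the range.**
- If δ = 0 or r = 0, D = Δ and there is no bias. With no effect on symptoms or CT, D = 0.
- If quinine has no CT effect (Δ = 0) but lowers symptoms by 0.5 SD, D = r × [λ(t + 0.5) - λ(t)], which is 0.10 to 0.24 SD against quinine over the same grid.
- The table is post-treatment only, while the planned endpoint is pre and post. Suppose every patient had a baseline CT, correlated r₀ with week-12 symptoms. For a change score, r is replaced by r - r₀. With r₀ from r/2 to r, the case (b) loss runs from none to half the tabled figure, at most about 24%. With baseline adjustment under the same shifts, and an assumed pre/post correlation of 0.5 to 0.7, simulation gave 7-39%. But the plan does not provide a baseline CT for every patient.

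**Precision.** If the 10 non-randomized lead-in patients (Section 4.3) count in the 100 and the rest split evenly, there are (100 - 10) / 2 = 45 per arm. Applying one scan rate to both arms, the 95% half-width is t₀.₉₇₅ × √(2/n) SD: about 1.0 SD at 20% (n = 9), 0.60 SD at 50% (n = 22.5), and 0.42 SD if all 45 were scanned. If indications at the two visits were independent, paired scans would number 45 × 0.2² ≈ 2 or 45 × 0.5² ≈ 11 per arm.

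**The case against.** The strongest defence is that the plan is open about the limit. It states the condition on CT in five places, ranks CT as secondary, and makes the model's use of available data depend on unpatterned missingness. A reader might infer that a CT p-value will certainly be reported as though randomization protected it. The text does not go that far, because the condition in Section 6.5 could be taken as a reason to withhold the test. What survives is that the section applies the model to CT by default and names no alternative.

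It is also fair that no passage defines clinical indication or says that week-12 scans follow symptoms. That scanned patients are sicker is plausible, not documented. Bias needs treatment to affect what prompts the scan. That is close to the trial's hypothesis, since SNOT-22 is a primary outcome, but it is not certain. The direction could differ under other scanning patterns. In the scenarios run, selection hid a benefit or went against quinine, and none produced a false claim of efficacy.

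A reader might further infer from Section 4.4.2 that a patient without a CT is dropped from every analysis. The documents do not support that. The sentence stands under withdrawn subjects, Section 8.3 separates items not done from items not applicable, Section 6.5 uses all available data, and Section 6.6 analyses everyone randomized. The conflict between 4.4.2 and 6.5/6.6 is real but is a separate matter. Here it warrants only a clarifying sentence.

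**Conclusion.** The point holds as a gap in the analysis plan. A week-12 CT score exists only by a decision made after treatment, Section 6.5 models it by arm with everything else, and its own missing-data condition is likely to fail for this endpoint with nothing specified in its place. If quinine changes the symptoms that prompt a scan, the contrast is likely to be biased, most plausibly hiding a benefit or going against quinine.

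The size cannot be computed from the documents. Under the stated assumptions the loss is about 6-29% when symptoms move only through CT and about 21-49% when they shift by 0.5 SD. The upper range should not be quoted alone: it rests on that full symptom shift and a post-treatment-only comparison, and some pre/post analyses would lose less. No primary outcome and no sample-size figure depends on CT, so the priority is low to moderate.

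**What to change.** In Sections 3.3 and 6.5, label the Lund-Mackay score descriptive or exploratory. Report, by arm and visit, the number scanned and the scores, with no between-arm test and no efficacy claim. Leave the clinical indication for CT unchanged. Add one sentence stating that a CT that was not clinically indicated does not make a subject incomplete under Section 4.4.2. Make the change before unblinding.

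An indication-weighted or joint model with sensitivity analyses is an alternative. It would need the drivers of scanning to be recorded and would rest on few scans.

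The cost is wording only. The downside is that one secondary endpoint loses its formal test.

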3.4 Primary Safety Endpoints

- Tolerability (due to bitterness).

4 Subject Selection and Withdrawal

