1.5 Dose Rationale and Risk/Benefits

Our plan is to first study quinine against saline to determine efficacy and safety. The vast majority of patients with rhinosinusitis utilize low pressure / high volume (240mls) sinonasal lavage to cleanse the sinonasal cavity⁹. We propose to have the patients administer 6mls of quinine (1mg/ml) (same concentration that was used in the study mentioned above, which also activates NO production from human primary nasal cells *in vitro*) via a 3cc syringe with a mucosal atomizing device (MAD) on the tip. Patients will apply 3 mls to each nostril twice per day. Thus the patients will be exposed to a maximum of 12mls or 12.0 mg of quinine. In standard tonic water, quinine is 8.3mg/100mls and thus an 8oz glass of Canada Dry tonic water has 19.6mg of quinine. Thus, the maximum systemic exposure in our study (assuming ingestion of the total nasal administration) is less than drinking one glass of tonic water / day. To put this in context, the therapeutic range of quinine to treat malaria is 10mg/kg TID (2100mg for a 70kg individual) nearly 200 X the dose we are proposing.

We propose to enroll only patients who have had prior functional endoscopic sinus surgery (FESS) for two reasons: (1) better access to the sinonasal cavity to obtain microbiologic samples before, during and after the trial, and (2) patients with a marsupialized sinonasal cavity are not at risk for developing intra-orbital or intra-cranial complications from bacterial sinusitis, as a path of egress for the infection is widely patent into the nose.

2 Study Objectives

The overall objective of this study is to evaluate the efficacy of quinine nasal irrigations as a first line therapy for acute exacerbations of uncomplicated chronic rhinosinusitis following endoscopic sinus surgery.

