5.1 Description

IDS will compound 0.9% buffered sterile NaCl for irrigation with USP grade quinine to a 1mg/ml concentration. For the placebo arm, IDS will compound 0.9% sterile NaCl for irrigation with sucrose octaacetate (0.5mg/ml) to achieve the same degree of bitter taste as 1mg/ml concentration of quinine¹⁹.

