5.7 Packaging

1 mg/ml concentration of quinine in saline solution will be given to participants to instill in each nostril. Product will be packaged in 90mL amber glass boston rounds, which have been autoclaved prior to use. A pharmaceutical press-in bottle adapter will be inserted into the neck and a child-resistant cap tightly placed onto the bottle. Doses will be administered by use of an LMA® MAD NASAL™ Intranasal Mucosal Atomization Device with 3mL syringe and vial adapter (Teleflex Medical, Research Triangle Park NC; item # MAD140OS), which is patient-specific. Participants will do this twice per day for 4 weeks. Subjects will clean the mucosal atomization device after each use with an alcohol swab.

Blinding of Study Drug

The placebo arm will be spiked with Sucrose Octaacetate which has a bitter taste, but does not stimulate sinonasal NO production.

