7.2 Recording of Adverse Events

At each contact with the subject, the investigator must seek information on adverse events by specific questioning and, as appropriate, by examination. Information on all adverse events should be recorded immediately in the source document, and also in the appropriate adverse event module of the case report form (CRF). All clearly related signs, symptoms, and abnormal diagnostic procedures results should be recorded in the source document, though should be grouped under one diagnosis.

All adverse events occurring during the study period must be recorded. The clinical course of each event should be followed until resolution, stabilization, or until it has been determined that the study treatment or participation is not the cause. Serious adverse events that are still ongoing at the end of the study period must be followed up to determine the final outcome. Any serious adverse event that occurs after the study period and is considered to be possibly related to the study treatment or study participation should be recorded and reported immediately.

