7.5 Stopping Rules

The first 10 participants of the trial will be un-blinded to the attending physicians. They will monitor the clinical efficacy of the treatment, and analyze outcome measures to determine whether or not the trial should proceed or be aborted. The trial will continue if and only if no clinically significant adverse events are observed in the treatment and/or placebo arms.

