7.6 Medical Monitoring

It is the responsibility of the Sponsor to oversee the safety of the study at his site. This safety monitoring will include careful assessment and appropriate reporting of adverse events as noted above, as well as the construction and implementation of a site data and safety-monitoring plan (see section 10 Auditing, Monitoring and Inspecting). Medical monitoring will include a regular assessment of the number and type of serious adverse events.

CONFIDENTIAL

8 Data Handling and Record Keeping

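### The only primary safety endpoint is bitterness tolerability, which the placebo is formulated to match, and no between-arm analysis of the recorded adverse events is specified

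*Combined protocol and SAP*

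**What the plan says.** Safety is part of the stated question. The title names efficacy and safety, and section 1.5 says: "Our plan is to first study quinine against saline to determine efficacy and safety".

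Section 3.4 (Primary Safety Endpoints) has a single entry, "Tolerability (due to bitterness"). The placebo is sucrose octaacetate 0.5 mg/ml in saline, a concentration chosen (section 5.1) "to achieve the same degree of bitter taste as 1mg/ml concentration of quinine". The blinding text under section 5.7 adds: "The placebo arm will be spiked with Sucrose Octaacetate which has a bitter taste, but does not stimulate sinonasal NO production".

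Safety data are collected more widely than section 3.4 suggests. Under section 7.2, at each contact "the investigator must seek information on adverse events by specific questioning and, as appropriate, by examination", and "All adverse events occurring during the study period must be recorded". Section 7.6 states: "Medical monitoring will include a regular assessment of the number and type of serious adverse events". Section 7.5, which opens with the first 10 participants, states: "The trial will continue if and only if no clinically significant adverse events are observed in the treatment and/or placebo arms".

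Section 6.5 plans linear mixed-effects models for the outcome measures and names no adverse-event or tolerability analysis. Section 4.4.2 accepts that early withdrawal may reflect tolerability, then removes subjects with incomplete data from the analysis. Section 6.6 says that every randomized subject is analyzed.

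**The concern.** The one attribute named as the primary safety endpoint is the attribute on which the two solutions are meant to be alike. If the taste match succeeds, the arms should look the same on it whatever else quinine does in the nose. If the match fails, a difference would mainly reflect the formulation. Neither result describes harms other than taste.

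The adverse events, which do bear on the wider question, have no endpoint, summary measure or comparison attached. Read as written, the plan would let similar bitterness tolerability stand as its primary safety result, while the adverse-event comparison would be chosen after the data are seen. Section 4.4.2 adds a further risk: subjects who leave because they cannot tolerate the solution may be dropped from whatever comparison is made.

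**Working it through.** **1. The plan's own figure.** Section 6.4 gives 32 per group for a 95% interval half-width of 10 on SNOT-22 with SD 20.
- Normal formula: n = 2 × (1.96 × 20 / 10)² = 30.7, so 31.
- With the t distribution: n = 32, half-width 9.995.

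The figure reproduces. It concerns SNOT-22 only; the documents give no sample size or precision for safety.

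**2. Expected result on the section 3.4 endpoint.** If the match works, both arms share one intolerance rate p, and the expected difference is p − p = 0. A two-sided 0.05 test would then reject about 5% of the time, irrespective of quinine's other effects.

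The documents do not say whether the 10 non-randomized quinine subjects in section 4.3 count within the 100. Assume that they do and that the other 90 split equally, giving 45 per arm. The 95% half-width around zero is 1.96 × √(2p(1 − p)/45). The rates p are illustrative:

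| p | Half-width (percentage points) |
|---|---|
| 5% | 9.0 |
| 10% | 12.4 |
| 20% | 16.5 |
| 30% | 18.9 |

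**3. What adverse-event proportions could show, one arm.** With zero events among n subjects, the exact upper 97.5% limit is 1 − 0.025^(1/n).
- n = 45: 1 − 0.025^(1/45) = 7.9%.
- n = 32 (the section 6.4 minimum): 1 − 0.025^(1/32) = 10.9%.
- n = 55 (45 plus the 10 lead-in subjects): 1 − 0.025^(1/55) = 6.5%.

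These limits describe quinine exposure alone. They are not between-arm results.

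**4. What they could show, between arms.** Power at two-sided 0.05 with 45 per arm, for assumed true rates on placebo and quinine:

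| Rates | Normal approximation | Fisher exact |
|---|---|---|
| 5% vs 15% | 35% | 23% |
| 5% vs 20% | 58% | 48% |
| 5% vs 25% | 77% | 71% |

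Only large differences would be detected with reasonable probability.

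**5. The safeguards already in the plan.** Section 7.5 is tied to the first 10 participants. Section 4.3 places all of them on quinine, so they have no concurrent control. Zero events in 10 leaves a one-sided 95% upper limit of 1 − 0.05^(1/10) = 25.9%, and the chance of seeing at least one event of 10% incidence is 1 − 0.9^10 = 65%. Section 7.6 covers serious events only. Neither section sets out a comparison of randomized arms.

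**The case against.** A reader might infer that the randomized safety comparison cannot answer the safety question at all. The documents do not support that. Adverse events are actively sought and all are recorded, and nothing restricts this to one arm. A randomized comparison is therefore possible, and the bitter placebo helps it by protecting the blind. What is missing is its prespecification.

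A reader might also infer that the difference on the section 3.4 endpoint is zero by construction. That too is more than the text says. Section 5.1 states an aim, not a verified match. Equal average bitterness need not give equal tolerability over 28 days of twice-daily use, and the protocol itself tests individual bitter sensitivity at baseline. A residual difference could appear.

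Three further points deserve weight.
- Section 3.4 mentions no comparison. It can be read as asking whether patients tolerate a bitter solution at all, and matching does not empty that question. Even so, that reading leaves other harms unaddressed.
- Olfaction, SNOT-22 and endoscopy are endpoints and could reveal nasal worsening. The plan does not designate them as safety measures, and they do not replace adverse-event incidence.
- The sponsor gives reasons for a narrow focus: exposure put below one glass of tonic water a day, no adverse events reported in the two earlier studies described in section 1.4, and a trial meant to guide later ones. These bear on how much harm to expect. They do not remove the need to say how recorded events will be compared.

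**Conclusion.** The point holds in a limited form. The only listed primary safety endpoint is expected to show about no arm difference if the taste match works, and it says little about harms of quinine beyond taste. The adverse events that would say more are collected, but neither section 3.4 nor section 6.5 specifies a between-arm analysis of them. This is a defect in endpoint choice and prespecification, not a failure to collect safety data.

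The remedy has modest reach. Zero events of a given type on quinine would give an upper limit of 7.9% with 45 subjects or 10.9% with 32. The 45 rests on the two assumptions stated above, about the lead-in and the equal split. All event rates in the power figures are illustrative. Power is low for all but large differences, so intervals rather than tests should carry the conclusion. The change should be made, and it is cheap.

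**What to change.** In sections 3.4 and 6.5, add as safety endpoints the proportions of subjects with any adverse event, with a related adverse event, and discontinuing for an adverse event. Report them by randomized arm with an exact 95% interval for each arm and a confidence interval for the difference.

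Include all treated subjects, with those who withdraw, and state that the section 4.4.2 exclusion for incomplete data does not apply to safety. That exclusion also needs reconciling with sections 6.5 and 6.6. Show the 10 non-randomized lead-in subjects separately, and say whether they count within the 100.

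Keep bitterness tolerability as an acceptability and taste-match check, and define how it is measured, since the documents give no scale or assessment for it.

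The cost is wording and one extra table, with no added visits. Section 7.2 already requires the events to be recorded; the sponsor should confirm that the case report form captures relatedness and discontinuation for non-serious events too. The downside is low power for arm differences, and the text should say that the purpose is estimation.
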